#### Confidentiality Statement

This document is confidential and is to be distributed for reference only to study staff, human research ethics committees and the applicable regulatory authorities. Information is not to be reproduced, abstracted or used for sharing of information for any purpose without with the written permission of the [name] or his delegate.

---

**visits will be used to follow general progress focusing on tolerability, side effects and adherence. For the four weeks after the end of the treatment period, participants will enter the follow-up phase with a follow-up clinic visit on day 71 for final safety and efficacy assessment.**

### **3.2 Endpoints**

#### **3.2.1 Efficacy**

Primary

- Greater reduction in bacterial load relative to comparator

Secondary

- Reduced capacity of *PsA* to produce biofilm relative to comparator
- Reduced biofilm mass relative to comparator

Exploratory

- Greater reduction in MIC of *PsA* to Tobramycin and other antibiotics relative to comparator
- Greater reduction in evidence of inflammation relative to comparator
- Reduction in beta-lactamase production by *PsA*
- Greater clinical improvement relative to comparator (respiratory symptoms check and spirometry – FEV1)
- Differences in microbiome relative to comparator
- 

#### **3.2.2 Safety**

- No adverse effect on respiratory symptoms or lung function.
- No evidence of systemic reaction or side effects.

### **3.3 Randomisation**

**The pharmacist prior to commencement of the study will prepare a permuted-block randomisation schedule. The statistician will hold the full randomisation code so that all investigators, study staff and participants remain blinded. Access to a patient's allocated treatment will be available in a sealed envelope kept in the pharmacy with the investigational product should there be a need for unblinding.**

### **3.4 Investigational Product**

The Investigational Product is the Calcium form of disodium ethylene diaminetetraacetate (Ca-EDTA). Investigational product will be manufactured and stored in the Princess Margaret Hospital Pharmacy Department.

#### **3.4.1 Active Study Drug**

---

#### **Confidentiality Statement**

This document is confidential and is to be distributed for reference only to study staff, human research ethics committees and the applicable regulatory authorities. Information is not to be reproduced, abstracted or used for sharing of information for any purpose without with the written permission of the [name] or his delegate.

---

Calcium disodium ethylene diaminetetraacetate (Ca-EDTA) TRIS-buffered to pH~7.1 in 1.5ml normal saline added to 2.5 ml Tobramycin solution to make a 50Mmol solution and nebulised four times daily for two weeks during the admission phase followed by two times daily for the four week outpatient phase.

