**(b) Local (respiratory) effects**

When considering the tolerability and local effects of inhaled medications, concentration rather than dose is the most appropriate consideration. This is the foundation of all inhaled challenge testing using doubling concentrations until a concentration is reached where provocation results in a measurable effect. The corollary of this principle is that a total dose inhaled over a short time (at a high concentration will result in provocation of local (respiratory) side effects, whereas the same dose, even given repeatedly, over a longer period (at lower concentrations) will not result in any adverse effects. After reviewing all the relevant literature, we have chosen to prescribe a 4ml solution of 50mM concentration of Ca-EDTA based on, amongst others, the studies presented here:

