**Eligible admitted patients will all receive our standard institutional regime of dual intravenous and twice daily nebulised antibiotic regime for 2 weeks while in hospital followed by four weeks of outpatient twice daily nebulised antibiotic (Tobramycin). At the discretion of the treating physician, some patients may also have oral antibiotics during the outpatient four week phase. The choice of intravenous antibiotics and (if necessary) any additional anti-bacterial and/or anti-fungal antibiotics (both intravenous and/or oral, and in and/or out of hospital) will be made on clinical and microbiological grounds by the treating physician and will not influence or be influenced by the trial. Thus the only medication change as a result of participating in the trial will be the randomised double-blinded addition of either Ca-EDTA or placebo (normal saline) to the nebulised antibiotic (Tobramycin) throughout the 6-week treatment period. Screening will take place on admission to hospital with the permission of the treating physician, and if the participant meets the inclusion and exclusion criteria, he/she will start Day 1 of the trial that same day or the next day with randomisation of study drug and baseline investigations. The study will involve 32 children aged equal to or >6 years and be divided into three phases – the hospital admission phase (during which both intravenous and nebulised antibiotics will be given; the outpatient phase (nebulised antibiotic phase); and the follow-up phase (safety and ongoing efficacy). During the 2-week intravenous phase of treatment (while admitted) participants will be given study treatment (Ca-EDTA or placebo) four times daily – twice daily combined with their inhaled antibiotic, and twice daily on its own in between the inhaled antibiotic doses. The rationale behind the two extra daily doses of Ca-EDTA (or placebo) during the intravenous phase is to increase the period of Ca-EDTA airway activity while antibiotic is being presented to the airway mucosa in a continuous fashion via the bloodstream over the 24 hour period of each day, in addition to the twice daily nebulised Tobramycin. Following discharge from hospital - during the 4 week outpatient phase - the participants will continue to receive study drug (inhaled Tobramycin with added Ca-EDTA or placebo) twice daily. Baseline assessments and measurements as well as safety and tolerability will be evaluated on Day 1 followed by safety and efficacy assessments weekly on Day 8 and Day 15) until discharge. Subsequent assessments in the outpatient phase will be by telephone call visits on Day 29, and a clinic visit on Day 43. Clinic visits will monitor safety and efficacy parameters while telephone call**

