### **3.4.2 Comparator**

TRIS-buffered normal saline 1.5ml added to 2.5 ml Tobramycin solution and nebulised four times daily during the two week admission phase followed by twice daily for the four week outpatient phase of the study.

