## **3.5 Duration of Therapy**

Study participants will receive Ca-EDTA or placebo in combination with Tobramycin nebulised twice daily from Day 1 through to Day 43. For the first two weeks while admitted to hospital, participants will receive an extra two doses of study drug (Ca-EDTA or placebo) mixed with normal saline (instead of the Tobramycin) in between the standard two doses mixed with Tobramycin (see above for explanation and rationale). Following discharge from hospital, subsequent doses will be self-administered twice daily in the participant's home for four weeks, unless the participant elects to discontinue treatment. After completion of the 42 day treatment period participants will be monitored for a further 28 days for safety and ongoing efficacy. Participants will continue in the study until all follow-up assessments are completed.

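### Sections 3.4.1 and 3.4.2 give the tobramycin mixture four times daily in hospital, but Sections 3.1 and 3.5 give tobramycin only twice daily

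*Protocol*

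**What the plan says.** Two descriptions of the inpatient regimen stand in the current protocol text.

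**Product definitions.** Section 3.4.1 has the Ca-EDTA solution "added to 2.5 ml Tobramycin solution to make a 50Mmol solution and nebulised four times daily for two weeks during the admission phase". Section 3.4.2 has the control as "TRIS-buffered normal saline 1.5ml added to 2.5 ml Tobramycin solution and nebulised four times daily during the two week admission phase". Both then go to twice daily for the four outpatient weeks.

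**Schedule.** Section 3.1 describes the background treatment as the "standard institutional regime of dual intravenous and twice daily nebulised antibiotic regime for 2 weeks while in hospital". It gives study treatment four times daily in hospital: "twice daily combined with their inhaled antibiotic, and twice daily on its own in between the inhaled antibiotic doses". Section 3.5 has "Ca-EDTA or placebo in combination with Tobramycin nebulised twice daily from Day 1 through to Day 43" and adds that in the first two weeks "participants will receive an extra two doses of study drug (Ca-EDTA or placebo) mixed with normal saline (instead of the Tobramycin").

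Section 3.1 also states that "the only medication change as a result of participating in the trial will be the randomised double-blinded addition of either Ca-EDTA or placebo".

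Section 5.1, on administration, describes only the mixture of 1.5 ml study solution with 2.5 ml tobramycin. It does not mention saline-mixed doses. The product rows of the synopsis likewise describe only the tobramycin mixture.

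**The concern.** Section 3.4 is where a reader looks for what each arm receives and how often. Taken as written, it puts tobramycin into all four daily inpatient nebulisations, whereas 3.1 and 3.5 put it into two. A pharmacist or nurse working from 3.4 and 5.1 would not learn that half the inpatient doses should contain no tobramycin. Section 3.8 also allows a child to go home on intravenous treatment with the rest of the inpatient trial drug, so families may be preparing these doses.

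At stake is a doubling of inhaled aminoglycoside in children who, according to Section 1.6.1, generally also receive an intravenous one. The literal reading would also make untrue the assurance in 3.1 that Ca-EDTA or placebo is the only change in medication caused by the trial, because standard care there is twice-daily nebulised antibiotic.

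**Working it through.** **Inputs**

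- Tobramycin strength and volume per dose: 500 mg in 5 ml, 2.5 ml withdrawn (Section 5.1).
- Duration: 14 inpatient days, then 28 outpatient days (synopsis, duration of treatment).
- Inpatient tobramycin doses per day: 4 under 3.4.1 and 3.4.2; 2 under 3.1 and 3.5.
- Outpatient tobramycin doses per day: 2 under every section.

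**Tobramycin per dose**

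500 mg / 5 ml × 2.5 ml = 250 mg.

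**Exposure per child under each reading**

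| Quantity | Sections 3.4.1 and 3.4.2 | Sections 3.1 and 3.5 |
|---|---|---|
| Inpatient, per day | 4 × 250 = 1,000 mg | 2 × 250 = 500 mg |
| Inpatient nebulisations with tobramycin | 4 × 14 = 56 | 2 × 14 = 28 |
| Inpatient total | 1,000 × 14 = 14 g | 500 × 14 = 7 g |
| Outpatient total | 500 × 28 = 14 g | 500 × 28 = 14 g |
| 42-day total | 28 g | 21 g |

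The inpatient ratio is 14 / 7 = 2. The course ratio is 28 / 21 = 1.33.

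**Which reading is intended**

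Section 3.1 gives a reason for the two extra daily doses: to lengthen Ca-EDTA activity in the airway while antibiotic arrives through the bloodstream. That argues for more Ca-EDTA, not more inhaled tobramycin. Section 3.5 names the diluent for those doses. Section 1.6.2(b) supports four daily doses for Ca-EDTA only: it says "we have chosen to prescribe a 4ml solution of 50mM concentration of Ca-EDTA", and its item on particle clearance argues that 50 mM four times a day should not accumulate. Nothing in 1.6.2 sets tobramycin at four times a day. Twice-daily tobramycin is therefore the intended regimen.

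**Volume of the saline-mixed dose**

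No section states it. It can be inferred from the 4 ml, 50 mM specification:

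- Ca-EDTA per 1.5 ml syringe: 50 mM × 4 ml = 0.2 mmol.
- With 2.5 ml saline: 0.2 mmol / (1.5 + 2.5) ml = 50 mM, as specified.
- With no diluent, as 3.1 could be read: 0.2 mmol / 1.5 ml ≈ 133 mM. Section 1.6.2(b) reports that 100 mM EDTA caused unacceptable coughing in some patients in preliminary work for the earlier CF study.

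The saline volume should therefore be written down along with the frequency.

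**The case against.** The best reply is that the protocol resolves the matter itself. Section 3.5 follows directly after 3.4.2 and says plainly that the extra doses are made up in saline. Section 3.1 gives the same schedule with its rationale. Section 3.4 opens by naming Ca-EDTA as the investigational product, so four times daily can be read as the frequency of Ca-EDTA, with the diluent of two doses left out. Inpatient doses are given by nursing staff under pharmacy monitoring, and Section 3.8 promises them a full explanation. No worksheet has been shown to carry the error. Section 1.6.1 calls systemic absorption of inhaled tobramycin insignificant and says blood levels are monitored routinely; Section 6 schedules serum levels at Visit 1.

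Much of this stands. The intended regimen is recoverable, the excess exposure arises only if staff follow 3.4 over 3.1 and 3.5, and the stated safeguards limit its consequence. No endpoint, sample size or analysis is affected.

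It does not remove the defect. Both 3.4.1 and 3.4.2 attach the frequency to a mixture that explicitly contains 2.5 ml of tobramycin, and 3.4.2 cannot be read as a statement about Ca-EDTA. Section 5.1, the other place dispensing staff would consult, takes 2.5 ml of tobramycin for each dose and offers no correction.

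**Conclusion.** The contradiction is real, and 3.4.1 and 3.4.2 are wrong as written. Followed literally, they double inpatient inhaled tobramycin and add 7 g per child, raising the 42-day total by a third. These figures assume that every dose is taken and that the inpatient phase lasts the planned 14 days.

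The consequence is bounded. The error is identical in both arms, so it does not bias the treatment comparison, and the protocol's own statements on absorption and blood-level monitoring limit the safety concern. It should be fixed because it is a wrong dosing rule in the section that defines the regimen. That twice-daily tobramycin is intended rests on two explicit and mutually consistent sections. The 2.5 ml saline volume is an inference from the 4 ml, 50 mM specification.

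**What to change.** - **Sections 3.4.1 and 3.4.2:** state that during admission two daily doses are 1.5 ml study solution plus 2.5 ml tobramycin, and two are 1.5 ml study solution plus 2.5 ml normal saline. During the outpatient phase both daily doses are mixed with tobramycin.
- **Section 5.1:** add the saline-mixed inpatient doses with their 2.5 ml volume, so that the instruction to withdraw tobramycin applies only to the tobramycin-mixed doses.
- **Section 3.1:** say that the two in-between doses are mixed with normal saline, so that they cannot be taken as undiluted.
- **Confirmation:** the investigator confirms both the twice-daily tobramycin schedule and the 2.5 ml saline volume. Pharmacy worksheets, and the instructions given to families on home intravenous treatment, are checked against them.

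The cost is a protocol wording amendment and a document check. No extra patients, visits or procedures are needed.

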### **3.4.2 Comparator**

TRIS-buffered normal saline 1.5ml added to 2.5 ml Tobramycin solution and nebulised four times daily during the two week admission phase followed by twice daily for the four week outpatient phase of the study.

## **3.5 Duration of Therapy**

Study participants will receive Ca-EDTA or placebo in combination with Tobramycin nebulised twice daily from Day 1 through to Day 43. For the first two weeks while admitted to hospital, participants will receive an extra two doses of study drug (Ca-EDTA or placebo) mixed with normal saline (instead of the Tobramycin) in between the standard two doses mixed with Tobramycin (see above for explanation and rationale). Following discharge from hospital, subsequent doses will be self-administered twice daily in the participant's home for four weeks, unless the participant elects to discontinue treatment. After completion of the 42 day treatment period participants will be monitored for a further 28 days for safety and ongoing efficacy. Participants will continue in the study until all follow-up assessments are completed.

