### **3.7.3 Replacement of Participants**

**Participants who prematurely discontinue from the study for any reason will not be replaced.**

## **3.8 Investigational Product Accountability and Disposition of Clinical Study Supplies**

**During the 2-week inpatient phase, an accountability log will be attached to each individual trial patient's medication chart with full explanation and documentation to nursing staff on administration and recording of trial drug. Should the patient be discharged on "Home IV", he/she will be given the remainder of the 2-week inpatient trial drug with full explanation of how it should be administered. At the 2-week review visit, the patient will be required to return all used and unused trial drug items, when pharmacy will perform a standard accountability log, before dispensing the 4-week outpatient batch of trial drug. At the 6-week review visit (4 weeks after cessation of IV antibiotic treatment)) the patient will again be requested to return all used and unused items for standard pharmacy accountability logging. A spare 3-day reserve supply will be issued to each patient to be kept separate from the main batch for use if the main batch is mislaid or damaged. Pharmacy will arrange appropriate**

---

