**Visit 3: (at discharge from hospital and end of IV antibiotic treatment)**

**(a) Safety:**

- **Respiratory signs and symptoms checked pre- and half hour post-dose**
- **Spirometry pre- and half hour post-dose**
- **Tolerability, adverse events and diary card check**
- **History, system examination and vital signs checked**
- **Safety blood tests performed**
- **Concomitant medications noted**
- **CF Questionnaire applied**
- **Medication for 4-week home treatment period dispensed with appropriate instructions regarding storage and use as per protocol provided and explained to parent/patient.**
- **Emergency plan and phone numbers provided in case of emergency**

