**Visit 5: (end of treatment visit – 4 weeks after discharge/6 weeks after starting treatment)**

**(a) Safety:**

- **Respiratory signs and symptoms checked**
- **Spirometry**
- **Tolerability, adverse events and diary card check**

---

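### For a child discharged early on Home IV, the protocol gives incompatible study-drug schedules, and its definitions of Visits 3 and 5 no longer agree

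*Protocol*

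**What the plan says.** **Dosing.** Section 3.1 reads "During the 2-week intravenous phase of treatment (while admitted) participants will be given study treatment (Ca-EDTA or placebo) four times daily" and then "Following discharge from hospital - during the 4 week outpatient phase - the participants will continue to receive study drug", at twice-daily frequency. Section 3.5 repeats the pattern: "For the first two weeks while admitted to hospital, participants will receive an extra two doses of study drug", then "Following discharge from hospital, subsequent doses will be self-administered twice daily in the participant's home for four weeks". Section 3.4 calls the first two weeks the admission phase. Section 3.5 also says that treatment runs from Day 1 to Day 43 and refers to a treatment period of 42 days. The synopsis splits this into 14 days alongside intravenous antibiotics and 28 days as an outpatient.

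Section 3.8 deals with a child discharged on Home IV: "he/she will be given the remainder of the 2-week inpatient trial drug with full explanation of how it should be administered". The child returns for the 2-week review, and the four-week outpatient batch is dispensed only then. Section 3.8 does not state a dosing frequency.

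**Visits.** The Table of Study Assessments sets Visit 3 at Day 15 ± 3 and Visit 5 at Day 43 ± 3, and lists Visits 2 and 3 among those held while the child is in hospital. Section 6 describes Visit 3 as "at discharge from hospital and end of IV antibiotic treatment" and Visit 5 as "4 weeks after discharge/6 weeks after starting treatment". Section 3.8 describes the 6-week review as "4 weeks after cessation of IV antibiotic treatment". The power statement in section 10.1.2 places the primary comparison at 6 weeks, which is Visit 5.

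**The concern.** Discharge, end of IV and Day 15 are treated as one event, but section 3.8 itself foresees a child for whom they differ. For that child, sections 3.1 and 3.5 change the phase at discharge and section 3.8 changes it at two weeks. Staff have no stated rule for choosing between them. Section 3.5 also conflicts with itself: four weeks counted from an early discharge stop short of its own Day 43 and 42-day period.

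Study-drug exposure, and to a lesser degree the date of the sputum specimens, could then vary with discharge practice. With 16 children per arm, a few handled differently would add noise to the 6-week comparison. The per-protocol population in section 10.1.2 requires at least 75% of doses, so the number of doses a child was meant to take has to be unambiguous.

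**Working it through.** **Inputs.** Four doses a day for 14 days, then two a day for 28 days (sections 3.1, 3.4, 3.5; synopsis). Windows of Day 15 ± 3 and Day 43 ± 3 (Table of Study Assessments). Per-protocol threshold of 75% of doses (section 10.1.2). The discharge day *d* is an assumption, since the protocol gives no distribution of discharge days and no Home IV frequency. I count *d* − 1 full inpatient days before discharge and take the full schedule as the denominator.

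**The plan's own figures.** 14 + 28 = 42 days, and 14×4 + 28×2 = 112 study-drug doses. With discharge on Day 15 every definition agrees: 112 doses, and Visit 5 on Day 15 + 28 = Day 43.

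**Three readings for discharge on Day *d*.**

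- A. The inpatient schedule continues to two weeks (inferred from section 3.8): 112 doses.
- B. Twice daily from discharge to the end of the 42 days (section 3.5 with its own end of treatment kept): 4(*d* − 1) + 2(43 − *d*).
- C. Twice daily from discharge, stopping after four weeks (the discharge sentence of section 3.5 taken alone): 4(*d* − 1) + 56.

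For *d* = 6:

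- A: 112.
- B: 5×4 + 37×2 = 94, and 94/112 = 83.9%.
- C: 5×4 + 28×2 = 76, and 76/112 = 67.9%.

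The step from A to B is the frequency conflict, 9 days × 2 = 18 doses. The step from B to C is the earlier stop, another 9 × 2 = 18.

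| Discharge | A | B | C | Discharge + 28 days |
|---|---|---|---|---|
| Day 6 | 112 | 94 (83.9%) | 76 (67.9%) | Day 34 |
| Day 8 | 112 | 98 (87.5%) | 84 (75.0%) | Day 36 |
| Day 10 | 112 | 102 (91.1%) | 92 (82.1%) | Day 38 |
| Day 12 | 112 | 106 (94.6%) | 100 (89.3%) | Day 40 |
| Day 15 | 112 | 112 | 112 | Day 43 |

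**Per-protocol threshold.** 0.75 × 112 = 84 doses. Even twice-daily dosing on all 42 days gives 42×2 = 84, which still meets the threshold. The frequency conflict alone therefore cannot take a fully adherent child below it. Only reading C can, when 4(*d* − 1) + 56 < 84, that is, for discharge before Day 8.

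**Visit dates.** Visit 5 counted from discharge is Day *d* + 28. It lies within Days 40 to 46 when *d* ≥ 12, so the window absorbs discharge on Days 12 to 14. Visit 3 held at discharge likewise lies within Days 12 to 18 only when *d* ≥ 12. For a child who completes a 14-day IV course at home, end of IV plus four weeks is again Day 43, so the discharge anchor is the one that departs. The dosing conflict has no such tolerance and exists for any discharge before Day 15.

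**The case against.** The strongest reply is that section 3.8 is the specific provision for Home IV, while sections 3.1 and 3.5 describe the usual inpatient course. Section 3.1 ties the extra doses to the intravenous phase and the synopsis ties the 14 days to intravenous antibiotics, so the intent may be clear. This has some weight. However, section 3.8 concerns drug accountability, gives no frequency, and is not mentioned in sections 3.1, 3.4 or 3.5, which limit the extra doses to the admission. Continued four-times-daily dosing is a reasonable inference from section 3.8 but is not stated there.

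A second reply is that Visit 5 is fixed well enough by Day 43 and by six weeks from the start of treatment, the discharge and end-of-IV phrases being glosses on the usual case. This largely stands: the 6-week anchor dominates. It is weaker for Visit 3, whose description in section 6 carries no study day.

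A reader might infer three stronger conclusions that the documents do not support:

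- **Early discharge drops a child out of the per-protocol population.** This needs reading C, which disregards the Day 43 and 42-day statements in section 3.5.
- **The trial has two competing primary-endpoint dates.** No text calls a visit around Day 34 the 6-week visit.
- **IV courses longer than 14 days cause the same trouble.** The stated durations are two weeks or 14 days throughout; only Home IV is foreseen.

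**Conclusion.** The contradiction is real and confined to children discharged on Home IV before two weeks. For them the protocol supports at least two study-drug schedules, which differ by 2 × (15 − *d*) doses: 18 of 112 for an assumed discharge on Day 6, and 6 for Day 12. A larger gap appears only if treatment is also cut to four weeks after discharge, against section 3.5's own end of treatment. Visits 3 and 5 carry definitions that disagree for these children, and the difference exceeds the visit window only for discharge before Day 12.

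The consequence is inconsistent exposure and specimen timing, that is, noise. Allocation is randomised and blinded, and nothing here shows bias between the arms. The sample-size calculation is unaffected. How much this matters depends on how many children go home on IV and how early, which the protocol does not state.

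**What to change.** Reconcile sections 3.1, 3.4, 3.5 and 3.8 into one stated rule for when the phase changes, and when treatment ends, in a child discharged on Home IV before two weeks. Which rule applies is for the sponsor to decide. State the resulting number of scheduled doses so that the 75% criterion has a defined denominator.

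Separately, anchor the Visit 3 and Visit 5 assessments and sputum specimens to days since the first study dose, Day 15 ± 3 and Day 43 ± 3 as already in the Table of Study Assessments. Remove the discharge and end-of-IV definitions of those visits from sections 3.8 and 6. Because outpatient drug is dispensed at Visit 3, say explicitly that fixing the visit day does not settle the dosing rule, and align dispensing with whichever rule is chosen.

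The cost is protocol wording. Home IV children would need to attend for Visits 2 and 3. Section 3.8 already requires a 2-week return, so the added burden is essentially the Day 8 attendance.
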